## SYNOPSIS

Name of Sponsor/Company: CytRx Corporation	
Protocol Number: ALDOXORUBICIN-P1/2-STS-03	Phase of Development: 1b/2
Title of the Protocol: An Open-Label Phase 1/2 Study to Investigate the Preliminary Safety and Activity of Aldoxorubicin plus Ifosfamide/Mesna in Subjects with Metastatic, Locally Advanced, or Unresectable Soft Tissue Sarcoma	
Primary Objectives: The primary objective of this study is to determine the preliminary safety of administration of aldoxorubicin in combination with ifosfamide in subjects with metastatic, locally advanced, or unresectable soft tissue sarcoma as measured by the frequency and severity of adverse events (AEs), abnormal findings on physical examination, laboratory tests, vital signs, echocardiograms (ECHO) or multiple-gated acquisition (MUGA) scans, electrocardiogram (ECG) results, and weight.	
Secondary Objectives: The secondary objective of this study is to evaluate the activity of aldoxorubicin in combination with ifosfamide/mesna in this population, assessed by overall response rate, progression-free survival (PFS) and PFS at 4 and 6 months.	
Study Rationale and Significance: Aldoxorubicin is a novel prodrug that binds covalently to albumin in the circulation. The drug is accumulated in tumors and doxorubicin is released in the tumor by cleaving the acid labile linker (EMCH) in the low pH tumor environment. This carrier-linked prodrug has demonstrated enhanced anti-tumor activity with reduced toxicity in several murine models and in patients with soft tissue sarcomas when compared with free doxorubicin.  Patients with metastatic, locally advanced, or unresectable soft tissue sarcomas have a poor prognosis with progression-free survival of around 4-5 months and median overall survival of approximately 15 months after treatment with single agent doxorubicin. Several chemotherapy regimens have been explored as palliative therapy for subjects with advanced soft tissue sarcomas. Combinations of ifosfamide and doxorubicin appear to offer the highest response rates and longest time to progression. However, as currently administered these regimens are quite toxic and have not significantly increased survival in these individuals. Aldoxorubicin in combination with a less toxic schedule for administering ifosfamide may improve the activity of this combination without increasing its toxicity as has been demonstrated for ifosfamide as a single agent.	

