The study is being expanded to further evaluate both the safety and efficacy observed to date with this combination. Seven subjects were enrolled in the aldoxorubicin (170 mg/m  ) + ifosfamide/mesna dose group without any dose-limiting toxicities. Similarly, 17 subjects have been enrolled in the aldoxorubicin (250 mg/m  ) + ifosfamide/mesna dose group without any dose-limiting toxicities. The most common Grade 3/4 adverse events across both cohorts have been neutropenia and anemia, both medically manageable. To date, there have been 6 subjects with confirmed partial responses and 10 subjects with stable disease across both dose groups. Ten additional subjects, for a total of 40 subjects, will be added across two cohorts: 1) 250 mg/m  aldoxorubicin + ifosfamide/mesna (10-14 days) dose group in previously untreated subjects (current study design), and 2) 250 mg/m  aldoxorubicin + ifosfamide/mesna at a dose of 1 gm/m  for up to 10 days in previously treated subjects.	
The aldoxorubicin 250 mg/m  + ifosfamide/mesna dose group is being expanded a second time to further assess the preliminary activity and safety of this combination. Thirty-one (31) subjects (22 first-line and 9 previously treated) have been enrolled in the aldoxorubicin (250 mg/m  ) + ifosfamide/mesna dose group without any dose-limiting toxicities. The most common Grade 3/4 adverse events have been neutropenia and anemia, both medically manageable. To date, there have been 4 subjects with confirmed partial responses and 13 subjects with stable disease in the 250 mg/m  + ifosfamide/mesna dose group. Forty additional subjects, for a total of 80 subjects (73 in the 250 mg/m  + ifosfamide/mesna dose group), will be added equally (20 subjects per cohort) across two cohorts: 1) 250 mg/m  aldoxorubicin + ifosfamide/mesna (10-14 days) dose group in previously untreated subjects (current study design), and 2) 250 mg/m  aldoxorubicin + ifosfamide/mesna at a dose of 1 gm/m  for up to 10 days in previously treated subjects.	

Name of Sponsor/Company: CytRx Corporation	
Protocol Number: ALDOXORUBICIN-P1/2-STS-03	Phase of Development: 1b/2

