Adjunctive Therapy, Dose and Mode of Administration: Mesna Injection is a sterile, nonpyrogenic, aqueous solution of colorless to light pink appearance in clear glass multidose vials for intravenous administration. Mesna injection contains 100 mg/mL mesna, 0.25 mg/mL edetate disodium, sodium hydroxide for pH adjustment and q.s with Water for Injection. Mesna injection multidose vials also contain 10.4 mg/mL of benzyl alcohol as a preservative. The solution has a pH range of 6.5 to 7.4.	
Criteria for Evaluation: 
Activity:  The following activity variables will be evaluated as noted:
 
 
• Progression-free survival
 
• Objective tumor response (RECIST 1.1 criteria)
 
• 4 and 6 month progression-free survival
 
	

Name of Sponsor/Company: CytRx Corporation	
Protocol Number: ALDOXORUBICIN-P1/2-STS-03	Phase of Development: 1b/2
Safety: The following safety variables will be assessed over the duration of the study: 

• Adverse events

• Ability to remain on assigned treatment (tolerability)

• Clinical and laboratory data including physical examinations, vital signs, weight, MUGA/ECHO, ECG results and laboratory test results

• Use of concomitant medications

	
Statistical Methods: In accordance with the modified intention-to-treat principle, all enrolled subjects who enter active treatment and have had at least 1 dose of study medication and 1 post-dose efficacy measurement will be included in the primary efficacy analyses.	

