Activity: Tumor response will be monitored every 8 weeks ( $\pm 5$ days) from Cycle 1-Day1 through week 32, and then every 12 weeks ( $\pm 5$ days) until disease progression. Objective response will be evaluated using the Response Evaluation Criteria In Solid Tumors 1.1 (RECIST 1.1).  Changes (i.e., improvements) in tumor measurements from baseline values will be assigned a status of CR or PR. Objective response measurements will comprise the sum of CR plus PR. The overall response rate, as well as the rates for the individual categories of response (i.e., CR, PR, SD, and PD), will be estimated by the percentage of subjects achieving these criteria. For the estimation of progression-free survival a Kaplan-Meier analysis will be performed. The percentage of subjects with complete or partial responses, or stable disease will be evaluated at 4 and 6 months.	
Safety: The safety data will be summarized by treatment group. Total number of AEs leading to withdrawal, and abnormal laboratory tests will be summarized for each cohort. Adverse events, ability to remain on assigned treatment (tolerability), and abnormal findings on physical examinations, vital signs, weight, ECG results, laboratory test results, and use of concomitant medications, will be assessed to characterize the safety profile of the treatment groups. Descriptive statistics denoting the changes from baseline to the final assessment visit with respect to key laboratory parameters and vital signs will also be provided.	

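### The primary efficacy set requires a post-dose measurement, so on the natural reading treated but never-assessed subjects leave the ORR and CR/PR/SD denominators, which can only raise those rates

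*Combined protocol and SAP*

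**What the plan says.** All references are to the current synopsis, the version that allows up to 80 subjects. Under Statistical Methods it invokes a modified intention-to-treat principle. The primary efficacy analyses include "all enrolled subjects who enter active treatment and have had at least 1 dose of study medication and 1 post-dose efficacy measurement".

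The Activity paragraph under the same heading says that the overall response rate, "as well as the rates for the individual categories of response (i.e., CR, PR, SD, and PD"), will be estimated as a percentage of subjects. It continues: "The percentage of subjects with complete or partial responses, or stable disease will be evaluated at 4 and 6 months". For PFS: "For the estimation of progression-free survival a Kaplan-Meier analysis will be performed". It names no separate denominator, lists no not-evaluable category, and has no rule for treated subjects without an assessment.

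Tumour assessment is every 8 weeks, give or take 5 days, from Day 1 of Cycle 1. Appendix A also schedules imaging at End of Treatment. Study Design and Methodology adds follow-up for subjects who stop without progression and start no other therapy.

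On weight, "The secondary objective of this study is to evaluate the activity of aldoxorubicin in combination with ifosfamide/mesna in this population", while the primary objective is safety. Study Design and Methodology nevertheless calls PFS, and PFS at 4 and 6 months, other primary objectives.

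**The concern.** The set has two entry conditions: a dose and a later efficacy measurement. The second is known only after treatment starts. A subject who dies, withdraws or is lost before any scan fails it and drops out of the denominator. That subject could not have been in the numerator, because CR, PR and SD all need an assessment. The exclusion therefore works in one direction on ORR and on the CR/PR/SD percentages.

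There is no control arm in which the effect could cancel, and the second expansion was undertaken partly to assess activity further. Enrolling more subjects narrows the interval around the rate but does not remove the shift. The plan does not call for a count of those excluded, so a reader of the results could not undo it.

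**Working it through.** The plan states no target ORR, power calculation or expected number of unassessed subjects, so there is no figure of its own to reproduce. The check is a comparison of denominators.

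**Inputs from the documents**
- Planned size: "Forty additional subjects, for a total of 80 subjects", of whom 73 are in the 250 mg/m² group.
- Interim status at 250 mg/m²: "Thirty-one (31) subjects (22 first-line and 9 previously treated) have been enrolled", with 4 confirmed PR and 13 SD.
- First expansion, both dose groups: 7 + 17 = 24 enrolled, 6 confirmed PR.

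**Assumptions**
- True ORR of 20%. This lies between the two interim figures, 4/31 = 12.9% and 6/24 = 25.0%.
- Share never assessed, e = k/N, of 3% to 10%. No document gives it.
- Enrolled subjects are taken as treated.

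**Formula.** Let x be the number of responders, N the number treated and k the number treated but never assessed. The all-treated rate is x/N. The rate on the plan's set is x/(N-k). The ratio is N/(N-k) = 1/(1-e). It exceeds 1 for every k above zero and equals 1 only if everyone is assessed.

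**Assumed ORR of 20%**

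| Share excluded | Rate on the plan's set |
|---|---|
| 3% | 0.20/0.97 = 20.6% |
| 5% | 0.20/0.95 = 21.1% |
| 8% | 0.20/0.92 = 21.7% |
| 10% | 0.20/0.90 = 22.2% |

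The shift is 0.6 to 2.2 percentage points.

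**Scale against sampling error.** With N = 73, the standard error is sqrt(0.20 × 0.80/73) = 4.7 points. The shift is 0.6/4.7 = 0.1 to 2.2/4.7 = 0.5 standard errors. The exact 95% interval for 15/73 is 12.0% to 31.6%.

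**Interim counts.** This is arithmetic only. The group is still enrolling, and the text does not say whether anyone lacked a scan.

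| Excluded | ORR | PR plus SD |
|---|---|---|
| 0 | 4/31 = 12.9% | 17/31 = 54.8% |
| 1 | 4/30 = 13.3% | 17/30 = 56.7% |
| 3 | 4/28 = 14.3% | 17/28 = 60.7% |

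The exact 95% intervals with nobody excluded are 3.6% to 29.8% and 36.0% to 72.7%. PR plus SD is a to-date count, not the 4- or 6-month percentage. Because the factor is a multiplier, the shift in points is larger for the CR/PR/SD percentage than for ORR.

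**The case against.** **The set may not govern ORR.** It is defined for the primary efficacy analyses, whereas ORR is listed only as secondary, and the Activity paragraph does not name its denominator. That is correct, and applying the set to ORR is an inference. It remains the natural reading, because the supplied text defines no other efficacy set.

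**Definitions may lie elsewhere.** Only synopses and schedules are available. Appendix A points to a Section 6 that is not supplied, and the term efficacy measurement is undefined. If death or clinical progression counts as a measurement, k shrinks. This stands as a limit on the finding.

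**The number excluded may be trivial.** A reader might infer that everyone who stops before week 8 is dropped. The documents do not support that, because subjects with an End of Treatment or follow-up scan stay in. Only those with no post-dose assessment at all are affected.

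**Missing assessments need not reflect outcome.** Missed visits or withdrawn consent can cause them too. If all were unrelated to outcome, the measured set would estimate the rate had everyone been scanned. The inflation shown here is therefore relative to the all-treated rate. Losses through early death are unlikely to be unrelated to response, and the plan has no rule that separates the two kinds.

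**A reader might infer that PFS is inflated as well.** That requires death to be a PFS event and not to count as an efficacy measurement. The supplied text says neither. Living, event-free subjects without a scan would be censored at Day 1, so including or omitting them leaves the Kaplan-Meier estimate unchanged. Nor can such an effect be bounded from the quoted "progression-free survival of around 4-5 months and median overall survival of approximately 15 months after treatment with single agent doxorubicin". That reference concerns single-agent doxorubicin, whereas 9 of the first 31 subjects at 250 mg/m², and half of the 40 added, are previously treated.

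**The weight is low.** Safety is the primary objective, no efficacy threshold or test is stated, and the set is openly labelled as modified. All of this stands.

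**Conclusion.** The point holds on the reading that the stated set supplies the denominator for ORR and CR/PR/SD. Following the plan as written then raises these rates by N/(N-k) relative to the all-treated rate whenever any treated subject goes unassessed. The direction follows from the definition. The size is not established, because k is unknown and may be zero.

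Under the assumed 20% ORR and 3% to 10% unassessed, the shift is 0.6 to 2.2 points. That is small beside sampling error, and no stated decision turns on it. It is still worth correcting, because the shift is systematic, more subjects do not reduce it, and avoiding it needs no new data. No claim is made about the size, or even the existence, of a PFS bias.

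**What to change.** - Estimate ORR and the CR/PR/SD percentages on all subjects who receive at least 1 dose.
- Add a not-evaluable row beside CR, PR, SD and PD. Place subjects with no post-baseline assessment there, counted as non-responders and as not CR/PR/SD at 4 and 6 months.
- Keep the present set as a labelled sensitivity analysis, and define what counts as an efficacy measurement.
- Report, per cohort, how many treated subjects had no post-baseline assessment and why.
- Use the same all-treated set for PFS. State that death before the first scan is an event and that living, event-free subjects without a scan are censored at Day 1.

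The cost is a few sentences in the statistical methods, one table row and a short count per cohort. No visits, subjects or data are added. The reported rates become slightly less favourable.

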## APPENDIX A: Schedule of Treatment and Evaluations

	Screening -21 Days	Day 1 of each Cycle	Day 4 of each Cycle**	Day 8 of each Cycle	Day 11 of each Cycle**	Day 10-11 of each Cycle 	Day 11-15 of each Cycle 	Day 21 of each Cycle	At end of every even Cycle	Every 8 weeks from Day 1 Cycle 1	Aldox Maintenance 	End of Treatment 	Every 2 or 3 mo. 
Signed informed consent	X												
Review inclusion/exclusion		X											
Medical history 	X												
Physical examination	X	X									X	X	X
Height (cm)	X												
Weight (kg)	X	X									X		
BSA calculation 		X									X		
Vital signs 	X	X									X	X	X
ECOG PS	X	X									X	X	
CT/ MRI scan / tumor measurements 	X 8a									X 	X 	X 	X
ECG	X	X									X	X	X
ECHO (with ejection fraction) or MUGA	X								X 		X 	X	X
CBC w/differential & plt 	X	X		X	X		X	X			X 	X 	X
Coagulation tests (PT, PTT, INR)	X												
Serum chemistries 	X*	X		X 			X 	X 			X 	X 	
Urinalysis 	X											X 	
Serum/urine pregnancy test	X												
Aldoxorubicin and ifosfamide/mesna administration 		X											
Aldoxorubicin administration											X		
Re-fill infusion pump, provide IV anti-emetics and hydration therapy, if necessary			X	X	X								
Stop infusion pump						X	X						
Filgrastim or pegfilgrastim administration 						X	X						
Concomitant medications	X 	X									X	X	
Adverse events		X									X	X	

**NOTE: All assessments must be performed within 72 hr of each specified time parameter, except Cycle 1 (see Section 6 for details).**

\*Arterial blood gas test may be done, if needed, to confirm acid levels. \*\*±2 days
